#### 4.2.4 Methods of Pooling Data

Data from all sites will be pooled for all analyses unless otherwise specified.

#### 4.2.5 Adjustments for Covariates

The primary analysis will include the randomization strata collected from eCRF as the stratification factors. For the analyses of all subjects, these stratification factors include ESR1-mutation status (ESR1-mut vs ESR1-mut-nd), prior treatment with fulvestrant (yes vs no), and presence of visceral metastases (yes vs no). For the analyses of ESR1-mut subjects and ESR1-mut-nd subjects, the stratification factors include prior treatment with fulvestrant (yes vs no) and presence of visceral metastases (yes vs no).

#### 4.2.6 Multiple Comparisons/Multiplicity

To ensure the family-wide error rate does not exceed 5%, multiplicity adjustments will account for the analyses of 2 primary endpoints, 2 key secondary OS endpoints, and the analyses of the key secondary OS endpoints at 2 time points. As described below, a truncated Hochberg procedure will be used to test the primary endpoints. The outcome of the analysis of the 2 PFS primary endpoints will determine

Sponsor:	Radius		
Protocol:	RAD1901-308		
Document Version No.:	1.1 (Final)	Document Date:	10-MAY-2021

the amount of alpha that will be passed to the analyses of OS. A Haybittle-Peto rule will be used to adjust the alpha for the analyses of OS at 2 time points.

The null hypothesis for the primary endpoint in ESR1-mut subjects is that elacestrant does not differ from the SOC treatment group in the IRC-assessed PFS for the ESR1-mut subjects; the alternative hypothesis is that elacestrant differs from the SOC treatment group in the IRC-assessed PFS for the ESR1-mut subjects.

The null hypothesis for the primary endpoint in all subjects (ESR1-mut and ESR1-mut-nd) is that elacestrant does not differ from the SOC treatment group in the IRC-assessed PFS for all subjects (ESR1-mut and ESR1-mut-nd); the alternative hypothesis is that elacestrant differs from the SOC treatment group in the IRC-assessed PFS for all subjects (ESR1-mut and ESR1-mut-nd).

OS is planned to be analyzed at the following 2 time points:

- x At the time of the primary PFS analysis (when approximately 160 and 340 PFS events are observed among the ESR1-mut and all subjects (ESR1-mut and ESR1- mut-nd), respectively, and
- x At the time of the final OS analysis (when approximately 50% of the subjects have died)

Although the sample size estimates were based on the conventional Hochberg procedure, a parallel gatekeeping strategy based on the truncated Hochberg procedure ([Dmitrienko et al. 2011](#)) will be used to control the family-wise type I error rate at 5% (2-sided) and to allow alpha to pass along from the analyses of the primary endpoint of PFS to the analyses of the key secondary endpoint of OS. The endpoint-specific alpha levels for the conventional Hochberg for this case are 0.05 and 0.05/2, and those for the equally weighted Bonferroni method are 0.05/2. The primary endpoint-specific alpha levels for the truncated Hochberg are constructed by combining the endpoint-specific alpha levels of the 2 methods with a truncation fraction. The analyses will use a truncation fraction of 0.9:

$$\alpha = 0.05 * 0.9 + 0.05/2 * (1-0.9) = 0.0475$$

$$\alpha = 0.05/2 * 0.9 + 0.05/2 * (1-0.9) = 0.025$$

To implement the truncated Hochberg procedure, the p-value for each of the 2 PFS primary endpoints will be derived without any adjustment. The larger p-value is  $\alpha_1 = 0.0475$ . If the larger p-value is not less than 0.0475, the smaller p-value is  $\alpha_2 = 0.025$ . If

- x If the larger p-value is  $< 0.0475$ , statistical significance will be claimed for both PFS endpoints. An alpha of 0.05 will be passed along to OS. To control for the analyses of OS at the 2 time points, the alpha level of 0.05 will be distributed across the 2 time points. A 2-sided alpha level of 0.0001 will be allocated at the time of the primary PFS analysis and a 2-sided alpha level of 0.0499 will be allocated at the time of the final OS analysis. This alpha splitting is according to a Haybittle-Peto rule. At each time point, OS will be evaluated using the conventional Hochberg

Sponsor:	Radius		
Protocol:	RAD1901-308		
Document Version No.:	1.1 (Final)	Document Date:	10-MAY-2021

procedure and the allocated alpha to control for the multiple testing associated with the 2 populations.

X If the larger p-value is  $< 0.025$ , statistical significance will be claimed only for the endpoint associated with the smaller p-value. An alpha of 0.0025 will be passed along to OS only in the population in which PFS is significant. To control for the 2 different times the OS analysis will be conducted, the alpha level of 0.0025 will be distributed across the 2 time points. An alpha level of 0.0001 will be allocated at the time of the primary PFS analysis and an alpha level of 0.0024 will be allocated at the time of the final OS analysis. This adjustment is according to a Haybittle-Peto rule.

X If the larger p-value is  $\geq 0.025$ , statistical significance will not be claimed. In this case, no alpha will be passed along to OS. No claim regarding OS will be made.

OS will be evaluated at 2 time points: (1) at the time of the primary analysis of PFS and (2) when approximately 50% of all subjects (ESR1-mut and ESR1-mut-nd) have died. At the time of this amendment, the study is fully enrolled (N=478). The second analysis of OS will take place when approximately 239 subjects have died. At the time of the PFS analysis, it is expected that approximately 96 subjects will have died.

Among all subjects (ESR1-mut and ESR1-mut-nd), the study will have 60% power to detect a hazard ratio of 0.75 at a 1-sided alpha level of 2.5%. Assuming a median OS of 25 months for the SOC treatment group, this hazard ratio represents a median OS of 33 months for the elacestrant treatment group. This calculation also accounts for 1 interim analysis at an information fraction of 0.4 with an alpha spending equal to 0.0001 at the interim analysis.

The study has enrolled 228 ESR1-mut subjects. Approximately 114 OS events are expected among the ESR1-mut subjects at the time of the second analysis of OS. With 114 OS events, the study will have 39% power to detect a hazard ratio of 0.73 at a 1-sided alpha level of 2.5%. Assuming a median OS of 28 months for the SOC treatment group, this treatment effect represents a median OS of 38 months for the elacestrant treatment group, an increase of approximately 10 months among the ESR1-mut subjects. This calculation also accounts for 1 interim analysis at an information fraction of 0.4 with an alpha spending equal to 0.0001 at the interim analysis.

Unless otherwise specified, analyses of all other efficacy endpoints will be performed at the 2-sided alpha level of 5% without adjusting the p-values for multiple comparisons.

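### The OS power figures in SAP 4.2.6 (60% and 39%) assume a stand-alone 1-sided 2.5% test that the SAP's own testing procedure never gives either OS endpoint

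*SAP*

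**What the plan says.** SAP 4.2.6 opens by saying that "multiplicity adjustments will account for the analyses of 2 primary endpoints, 2 key secondary OS endpoints", and also for the two OS time points. It then sets out three outcomes of the truncated Hochberg test of PFS:

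- **Both PFS endpoints significant.** Alpha of 0.05 passes to OS, split 2-sided as 0.0001 at the PFS analysis and 0.0499 at the final OS analysis. The two populations share it: "At each time point, OS will be evaluated using the conventional Hochberg" "procedure and the allocated alpha to control for the multiple testing associated with the 2 populations".
- **Only one significant.** "An alpha of 0.0025 will be passed along to OS only in the population in which PFS is significant". Of this, 0.0001 is used at the PFS analysis, and "an alpha level of 0.0024 will be allocated at the time of the final OS analysis".
- **Neither significant.** OS receives no alpha.

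The power statements follow. For all subjects (239 deaths), "the study will have 60% power to detect a hazard ratio of 0.75 at a 1-sided alpha level of 2.5"%. For ESR1-mut subjects (114 deaths), "the study will have 39% power to detect a hazard ratio of 0.73 at a 1-sided alpha level of 2.5"%. Each is qualified in one respect only: "This calculation also accounts for 1 interim analysis at an information fraction of 0.4", with 0.0001 spent there. SAP 4.1 refers the reader to 4.2.6 for the OS testing procedure and its power. SAP 6 explains that version 1.1 brought in the truncated procedure so that OS could still be tested when PFS succeeds in one population only.

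**The concern.** The power statements adjust for the interim look but not for the sharing of alpha between the two OS populations, nor for the dependence of OS alpha on the PFS result. A 2-sided level near 5% is available to an OS test only through the Hochberg step, when the other OS p-value is also below 0.0499. Otherwise the smaller p-value must be below 0.02495.

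These are the only power figures the plan gives for its key secondary endpoint. A colleague weighing a non-significant OS result would credit the test with more power than the procedure provides. No power at all is given for the one-population branch, which is the case version 1.1 was written to cover and the one where power is lowest.

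**Working it through.** **Inputs (SAP 4.2.6).** All subjects: 239 deaths, HR 0.75. ESR1-mut: 114 deaths, HR 0.73. Final OS level 2-sided 0.0499 (shared) or 0.0024 (one population). Allocation 1:1 (SAP 2.2). The SAP does not give the sidedness of 0.0024; I read it as 2-sided because the family-wise rate is 5% 2-sided.

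**Formula (Schoenfeld, 1:1).** Mean of the test statistic m = sqrt(d/4) × |ln HR|; power = Φ(m − z).

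- All subjects: m = sqrt(239/4) × 0.2877 = 2.224
- ESR1-mut: m = sqrt(114/4) × 0.3147 = 1.680

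**Step 1: the plan's own figures.** With z = 1.960:

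- All subjects: Φ(2.224 − 1.960) = 60.4%
- ESR1-mut: Φ(1.680 − 1.960) = 39.0%

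Simulating the 0.4-information look (0.0001, then 0.0499) leaves these unchanged. The stated figures are therefore single-test power.

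**Step 2: both PFS endpoints significant.** Hochberg at 0.0499 uses z = 1.961 if both OS p-values are below 0.0499, and otherwise z = 2.242 (2-sided 0.02495) for the smaller. Because the populations are nested, the correlation of the two OS statistics is sqrt(114/239) = 0.69. Power for one endpoint is the chance of passing 2.242 alone, plus the chance of falling between 1.961 and 2.242 while the other exceeds 1.961 (bivariate normal):

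- All subjects: 49.3% + 3.4% = 52.7%
- ESR1-mut: 28.7% + 8.0% = 36.7%

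A simulation that includes the interim look gives the same values. Moving the correlation from 0 to 0.8 gives 52–54% and 35–37%.

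**Step 3: only one PFS endpoint significant.** At 2-sided 0.0024, z = 3.036:

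- All subjects: Φ(2.224 − 3.036) = 20.8%
- ESR1-mut: Φ(1.680 − 3.036) = 8.8%

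Read as 1-sided, 0.0024 would give about 28% and 13%.

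**Step 4: dependence on the PFS result.** Steps 2 and 3 treat OS as independent of PFS. The documents give no correlation, so I assumed a range. PFS and OS statistics for both populations were simulated at the SAP's PFS design values (HR 0.667 with 340 events; HR 0.61 with 160 events) and the truncated Hochberg levels of 0.0475 and 0.025. Each cell shows all subjects / ESR1-mut.

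| Assumed PFS–OS correlation | Both PFS significant | Only that PFS endpoint significant | Overall, all branches |
|---|---|---|---|
| 0 | 52.7% / 36.7% | 20.9% / 8.7% | 47.1% / 31.6% |
| 0.2 | 54.4% / 38.5% | 16.5% / 7.0% | 48.2% / 33.2% |
| 0.4 | 56.1% / 40.2% | 12.1% / 4.9% | 49.3% / 34.6% |

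At those PFS effects the branch probabilities are: both 86.0%, all subjects only 8.6%, ESR1-mut only 0.9%, neither 4.5%. Check at zero correlation: 0.860 × 0.527 + 0.086 × 0.208 = 0.471 and 0.860 × 0.367 + 0.0088 × 0.088 = 0.316.

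**Step 5 (minor): the 114 deaths.** This is exactly half of 228, although the SAP assumes longer medians for ESR1-mut (28/38 months) than for all subjects (25/33 months). Assume exponential survival and, to show the arithmetic simply, equal follow-up t for everyone. Half of all subjects have died when the average of 2^(−t/25) and 2^(−t/33) is 0.5, at t = 28.6 months. ESR1-mut survival is then (0.492 + 0.593)/2 = 0.543, and 228 × 0.457 ≈ 104 deaths. Uniform accrual over 12 to 28 months (assumed) gives 104–105. With 105 deaths, ESR1-mut power is 34.2% in Step 2 (correlation 0.66) and 7.7% in Step 3.

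**The case against.** The best defence is that 60% and 39% are conventional single-test figures, correctly computed, with alpha, hazard ratio and interim look all stated. What is missing is a label. That stands as far as the arithmetic goes, but nothing in 4.1 or 4.2.6 says the figures precede the OS Hochberg and gatekeeping steps, and they sit directly beside those steps.

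It can also be said that Hochberg does compare an OS p-value with 0.0499. It does, but only when the other OS p-value is below 0.0499 too, which happens in about 34% of trials at the SAP's hazard ratios. The level is never unconditional.

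Three further points stand as limits. The ESR1-mut gap in the main branch is small and closes at a correlation of about 0.2 to 0.4, although overall ESR1-mut power stays at 32–35%. The one-population branch is uncommon at the planned PFS effects (8.6% plus 0.9%). The 0.0024 must be read as 2-sided to get 21% and 9%, though the 1-sided reading is still far below the stated power.

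Finally, enrolment is complete and no test or trigger depends on these figures. That limits the consequence to how OS results are read; it does not make the figures match the procedure.

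**Conclusion.** The concern holds. The stated OS power is that of a test the procedure does not perform. The firmest result is for all subjects in the main branch: about 53% against the stated 60%, and still only 54–56% with an assumed PFS–OS correlation of 0.2–0.4. For ESR1-mut the main-branch shortfall is about 2 points and not robust. In the one-population branch, for which the SAP gives no figure, power is about 21% or 9% at independence and about 12–17% or 5–7% at that correlation.

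These results rest on the SAP's own hazard ratios and event counts, proportional hazards, the nested-population correlation of 0.69 and a 2-sided reading of 0.0024. The event-count point is minor: about 105 ESR1-mut deaths rather than 114, under exponential survival and uniform accrual.

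**What to change.** In SAP 4.2.6:

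1. Label 60% and 39% as power for a single OS test at 2-sided 5%, before the OS Hochberg and gatekeeping steps.
2. Add power under the procedure. Both PFS endpoints significant: about 53% (all subjects) and 37% (ESR1-mut). Only one significant: about 21% if it is all subjects, or 9% if it is ESR1-mut, stating that 0.0024 is 2-sided. Neither significant: no OS claim.
3. State that these figures treat OS as independent of the PFS result, and that an assumed correlation of 0.2–0.4 moves them to about 54–56% and 39–40% in the first case, and to about 12–17% and 5–7% in the second.
4. Minor: use about 105 ESR1-mut deaths (ESR1-mut power then about 34% and 8%) or justify 114.

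The cost is SAP wording only. Tests, alpha, event triggers, sample size and patients are unaffected; the stated power becomes less favourable.

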Point mutations in the ligand-binding domain (LBD) of ER have been described as a potential mechanism of treatment resistance and as a poor prognostic factor in metastatic ER+ disease ([Chandarlapaty et al, 2016](#); [Fanning et al, 2016](#)). Two of the most frequently found estrogen receptor 1 gene (ESR1) mutations in patients, Y537S and D538G, have been shown to result in estradiol-independence and constitutive activation of ER in nonclinical models ([Li et al, 2013](#); [Toy et al, 2013](#); [Jeselsohn et al, 2014](#)). Furthermore, nonclinical studies have suggested that mutations in ER can cause decreased binding of ER antagonists to the receptor and a corresponding decrease in activity ([Fanning et al, 2016](#)). Recent clinical reports have demonstrated that some patients who have received AI therapy had detectable point mutations in ER ([Chandarlapaty et al, 2016](#); [Fribbens et al, 2016](#)). While the detection of ESR1-mut post-AI has been demonstrated clinically, the efficacy of AIs or fulvestrant in tumors harboring ESR1-mut has not been evaluated in a prospective clinical study where patients were stratified based on ESR1 status. The limited available clinical data are based on retrospective study designs with relatively small data sets, making it difficult to accurately predict hormonal agent activity against specific ESR1-mut or against tumors that harbor multiple ESR1-mut. Prospective studies stratified by ESR1-mut status will be critical in identifying the optimal therapeutic approach for subjects with tumors bearing ESR1-mut.

Next-generation, orally-bioavailable SERDs with improved PK properties have garnered significant interest as potential therapies for metastatic ER+ breast cancer in an effort to produce more durable clinical responses with a more favorable route of administration ([Bentzon et al, 2008](#); [McDonnell and Wardell, 2010](#); [Osborne and Schiff, 2011](#); [Glück, 2014](#)). Herein, the rationale for the proposed evaluation of elacestrant, a novel,

orally-bioavailable SERD for the treatment of ER+ breast cancer in a post-endocrine, post-CDK4/6 inhibitor setting, including patients who have tumors harboring ESR1 mutations, is described.

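### The OS power in SAP 4.2.6 is quoted at an alpha that its own testing rule does not give either population unconditionally, and the expected death counts do not fit the stated OS medians

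*SAP*

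**What the plan says.** SAP 4.1 points to SAP 4.2.6 for the OS testing procedure and for the OS power based on the deaths expected among the 478 enrolled subjects. SAP 4.2.6 then gives the following.

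- **All subjects:** final OS analysis at about 239 deaths; 60% power for a hazard ratio of 0.75 at 1-sided 2.5%; medians 25 months (SOC) and 33 months (elacestrant).
- **ESR1-mut:** "The study has enrolled 228 ESR1-mut subjects". The death count given for the final OS look equals half of that number: "Approximately 114 OS events are expected among the ESR1-mut subjects at the time of the second analysis of OS". The power sentence is conditional on that count: "With 114 OS events, the study will have 39% power to detect a hazard ratio of 0.73 at a 1-sided alpha level of 2.5" percent. The medians are 28 and 38 months ("Assuming a median OS of 28 months for the SOC treatment group").
- **First OS look:** "At the time of the PFS analysis, it is expected that approximately 96 subjects will have died". The calculations use one interim at information fraction 0.4, spending 0.0001.
- **If both PFS endpoints succeed:** 0.0499 (2-sided) is available at the final OS analysis, shared between the populations: "At each time point, OS will be evaluated using the conventional Hochberg" procedure.
- **If only one PFS endpoint succeeds:** OS is tested only in that population, and "an alpha level of 0.0024 will be allocated at the time of the final OS analysis".
- **If neither succeeds:** OS receives no alpha.

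On timing, Protocol 11.3.5 puts the PFS analysis at about 27 months, with 15 months of enrolment. Protocol 11.5 and SAP 4.1 put it at 30–33 months.

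**The concern.** The power figures and the testing rule stand in the same section but describe different tests. A 1-sided 2.5% test applied to each population alone is not what either success branch provides. The one-winner branch matters most: SAP 6 says the truncated Hochberg procedure was introduced so that OS could be tested when PFS is significant in only one population, yet no power is given for that case.

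The event counts raise a second question. 114 is exactly half of 228, and 96 is 0.4 × 239 (95.6). Neither is shown to come from the assumed medians. Because ESR1-mut subjects are assumed to live longer than all subjects, fewer than half of them should have died when half of all subjects have.

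At stake is what a reader expects from a key secondary endpoint under family-wise error control, and how much OS information the first look is thought to hold.

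**Working it through.** **Method.** Power = Φ(½√D × |ln HR| − z), where D is deaths, allocation is 1:1 and z is the critical value. |ln 0.73| = 0.3147 and |ln 0.75| = 0.2877. Survival is exponential at the stated medians. SAP 4.2.6 gives no accrual or dropout for OS, so I use the 15-month enrolment of Protocol 11.3.5 and vary it.

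**1. Reproducing the stated power (z = 1.960)**
- ESR1-mut, D = 114: 5.339 × 0.3147 = 1.680; Φ(−0.280) = 39.0% (stated 39%).
- All subjects, D = 239: 7.730 × 0.2877 = 2.224; Φ(0.264) = 60.4% (stated 60%).
- Adding the interim at fraction 0.4 changes either figure by less than 0.1 point.

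**2. Both PFS endpoints succeed: Hochberg at 0.0499**

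A population wins if its own 2-sided p is below 0.02495 (z = 2.242), or if both p-values are below 0.0499 (z = 1.961). The two statistics have correlation √(D/239): 0.691 for 114 ESR1-mut deaths and 0.660 for 104. The rescue term is the added chance of winning only through the both-below-0.0499 rule, from the bivariate normal distribution.

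| Population | Own test at 0.02495 | Rescue term | Power |
|---|---|---|---|
| All, 239 deaths | Φ(2.224 − 2.242) = 49.3% | 3.1–3.4 | 52.4–52.7% |
| ESR1-mut, 114 deaths | Φ(1.680 − 2.242) = 28.7% | 8.0 | 36.7% |
| ESR1-mut, 104 deaths | Φ(1.605 − 2.242) = 26.2% | 7.7 | 33.9% |

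**3. One PFS endpoint succeeds: 0.0024, z = 3.036**

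I take 0.0024 as 2-sided, because it comes out of the 2-sided 5%.
- All subjects: Φ(2.224 − 3.036) = 20.8%.
- ESR1-mut: Φ(1.680 − 3.036) = 8.8% with 114 deaths; Φ(1.605 − 3.036) = 7.6% with 104.

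**4. ESR1-mut deaths when 239 of 478 have died**

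With a common follow-up t, the fraction dead is 1 − 2^(−t/median).
- All subjects: at t = 28.64 months, 54.8% (median 25) and 45.2% (median 33), which average 50%.
- ESR1-mut at the same t: 50.8% (median 28) and 40.7% (median 38), average 45.7%. 228 × 0.457 = 104.
- With uniform accrual over 0–27 months and dropout of 0–10% a year, the range is 104.3–104.9. Half of ESR1-mut subjects would have died only at about 32.5 months.
- Power with 104 deaths at 1-sided 2.5%: Φ(1.605 − 1.960) = 36.1%.

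**5. Deaths at the PFS analysis**

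With uniform accrual over A months, the fraction dead at T is 1 − [e^(−λ(T−A)) − e^(−λT)]/(λA), where λ = ln 2/median. There are 239 subjects per arm.

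| T (A = 15) | SOC | Elacestrant | Deaths | Deaths/239 |
|---|---|---|---|---|
| 27 months | 41.3% | 33.3% | 178 | 0.75 |
| 30 months | 46.0% | 37.4% | 199 | 0.83 |
| 33 months | 50.3% | 41.2% | 219 | 0.92 |

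Using 25/0.75 = 33.3 months for elacestrant gives 218 in the last row. If accrual is assumed to last 27 months, the count at 27 months is 127 (fraction 0.53). Adding 20% dropout a year still leaves 110. With 15-month accrual, 96 deaths are reached at about 17 months.

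**6. Effect of the interim fraction on power.** Moving it from 0.4 to 0.9 changes ESR1-mut power by less than 0.1 point, because the interim spends only 0.0001.

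**The case against.** The strongest defence is that nothing in the power sentences is miscalculated. The 39% is expressly conditional on 114 events, and the alpha branches are set out openly in the same section. Quoting marginal power at full alpha is then a reporting choice. Neither 114 nor 96 enters a test, boundary or trigger: the looks are driven by PFS events and by about 239 total deaths, and enrolment is complete.

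Much of this stands. Four stronger readings are tempting, and the documents do not support them.

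- **That 39% is an arithmetic error.** It is correct for its own inputs.
- **That the 96-death mismatch lowers power.** It does not (step 6).
- **That the medians are right and the counts too high.** The documents do not settle this. If ESR1-mut survival were no better than overall, 114 or more deaths would be expected. The 96 may be a projection from pooled deaths in a fully enrolled trial; the SAP does not say.
- **That the longer ESR1-mut medians contradict the protocol.** Protocol 2.1 reports that such mutations have been described "as a poor prognostic factor in metastatic ER+ disease". That is background literature, and the same paragraph calls the clinical data limited. It is a tension with the medians and a reason to check them.

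The defence does not answer the alpha point. SAP 4.1 offers the section as the power of the OS analysis, and no branch of that analysis tests either population unconditionally at 1-sided 2.5%.

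**Conclusion.** The point holds in two parts.

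**Power by branch.** With both PFS endpoints successful, OS power is about 52% for all subjects (60% stated) and 34–37% for ESR1-mut (39% stated). With one successful, it is about 21% or 8–9%. The shortfall exists whether 104 or 114 deaths is right. These figures assume proportional hazards at the stated hazard ratios. They are power at each branch's alpha, without conditioning on the PFS result; overall power would also need the probability of each branch.

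**Event counts.** The medians and counts are mutually inconsistent. About 104 ESR1-mut deaths is robust to the accrual and dropout tried, and alone costs about 3 points (39% to 36%). The 96 deaths, and so the 0.4 information fraction, do not follow from the medians at 27–33 months under any accrual tried. The size of that gap depends on accrual, for which 15 months is the only documented value.

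Type I error control and the conduct of the analysis are unaffected.

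**What to change.** Amend the text of SAP 4.2.6:

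1. Report OS power for each alpha branch, for both populations, giving ESR1-mut over 104–114 events. Keep 39% and 60% only if labelled as power at a full 1-sided 2.5%.
2. State where 114 and 96 come from: the medians, a flat 50% and 40%, or a projection from pooled deaths.
3. Reconcile those counts and the 0.4 information fraction with the OS medians, and reconcile 27 with 30–33 months for the PFS analysis. Either the counts or the medians may be the figure to change.

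Enrolment, analysis triggers and tests stay as they are. The cost is a text revision and less favourable stated OS power.
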